Appendix B Exacerbations of Chronic Obstructive Pulmonary Disease Tool (EXACT)

[figure not shown]

Appendix C COPD ASSESSMENT TEST (CAT)
Appendix A COPD Assessment Test

[figure not shown]

[figure not shown]
COPD Assessment Test and the CAT logo is a trade mark of the GlaxoSmithKline group of companies.
© 2009 GlaxoSmithKline group of companies. All rights reserved.
Last Updated: February 24, 2012

Appendix D EUROQOL QUESTIONNAIRE (EQ-5D-5L)

[figure not shown]

USA (English) © 2009 EuroQol Group. EQ-5D™ is a trade mark of the EuroQol Group

[figure not shown]

[figure not shown]

[figure not shown]

Appendix F SGRQ Scoring Algorithm

Appendix G List of opportunistic infections

- Aspergillosis
- Blastomyces dermatitidis (endemic in the south-eastern and south-central states US, along Mississippi and Ohio Rivers)
- Candidiasis – only systemic or extensive mucosal or cutaneous candidiasis.
- Coccidioides immitis (endemic south-western US and Central and South America)
- Cryptococcus
- Cytomegalovirus
- Herpes Simplex (severe/disseminated)
- Herpes Zoster
- Histoplasmosis (pulmonary or disseminated; most common tropical areas Tennessee-Ohio-Mississippi river basins)
- Listeriosis
- Mycobacterium avium
- Nontuberculosis mycobacteria
- Pneumocystis pneumonia (PCP)
- Tuberculosis (TB)

This list is indicative and not exhaustive.

Appendix H Definition of anaphylaxis

“Anaphylaxis is a serious allergic reaction that is rapid in onset and may cause death.”

(Adapted from *Sampson HA, Munoz-Furlong A, Campbell RL, Adkinson NF, Bock SA, Branum A, et al. Second symposium on the definition and management of anaphylaxis: Summary report—Second National Institute of Allergy and Infectious Disease/Food Allergy and Anaphylaxis Network symposium. J Allergy Clin Immunol 2006;117:391-7*)

Clinical criteria for diagnosing anaphylaxis

[figure not shown]
Anaphylaxis is highly likely when any one of the following 3 criteria are fulfilled:

1. Acute onset of an illness (minutes to several hours) with involvement of the skin, mucosal tissue, or both (eg, generalized hives, pruritus or flushing, swollen lips-tongue-uvula)
AND AT LEAST ONE OF THE FOLLOWING
 - a. Respiratory compromise (eg, dyspnea, wheeze-bronchospasm, stridor, reduced PEF, hypoxemia)
 - b. Reduced BP or associated symptoms of end-organ dysfunction (eg, hypotonia [collapse], syncope, incontinence)
 2. Two or more of the following that occur rapidly after exposure to a *likely allergen for that patient* (minutes to several hours):
 - a. Involvement of the skin-mucosal tissue (eg, generalized hives, itch-flush, swollen lips-tongue-uvula)
 - b. Respiratory compromise (eg, dyspnea, wheeze-bronchospasm, stridor, reduced PEF, hypoxemia)
 - c. Reduced BP or associated symptoms (eg, hypotonia [collapse], syncope, incontinence)
 - d. Persistent gastrointestinal symptoms (eg, crampy abdominal pain, vomiting)
 3. Reduced BP after exposure to *known allergen for that patient* (minutes to several hours):
 - a. Infants and children: low systolic BP (age specific) or greater than 30% decrease in systolic BP*
 - b. Adults: systolic BP of less than 90 mm Hg or greater than 30% decrease from that person's baseline
-

PEF, Peak expiratory flow; BP, blood pressure.

*Low systolic blood pressure for children is defined as less than 70 mm Hg from 1 month to 1 year, less than (70 mm Hg + [2 × age]) from 1 to 10 years, and less than 90 mm Hg from 11 to 17 years.

Appendix I Low, medium and high dose of inhaled corticosteroids

Source: Adapted from Global Initiative for Asthma (GINA) 2017 guidelines

Appendix J Handling of missing data

Rate of AECOPD

The covariates in the model may change in different cases. The following code is for explanatory purposes only and that actual covariates included are as described in the main text of the SAP.

1. The following SAS code extracts samples from the posterior distribution of model parameters (including the dispersion parameter) using a Bayesian negative binomial log-link model with an offset variable which is equal to the log of the observed exposure time for each patient. Before doing so, we will need to digitalize all the variables in the model using

```
data ck1;set ck;
  txval=tx;
  stlval=0;
  if STRATUM1='LESS THAN 250 PER CUBIC MILLIMETRE' then stlval=1;
  reg1val=0;
  reg2val=0;
  if reg=1 then reg1val=1;
  if reg=2 then reg2val=1;
  mtx=txval;
  mst1=stlval;
  mreg1=reg1val;
  mreg2=reg2val;
  mx=xval;
run;
```

Note that 'xval' denote the other covariates that have been digitalized in the dataset and 'mx' denote is a copy of the covariates (we need this for technical reason). Then we can use the following Bayesian negative binomial model

```
proc genmod data=ck1;
  ods select PostSummaries PostIntervals;
  model aseq =mtx mst1 mreg1 mreg2 mx/ dist=negbin link=log
offset=logdur;
  bayes seed=17 nmc=10000 nbi=5000 coeffprior=normal outpost=ckout;
run;
```

2. For each draw (after thinning) the expected number of events is calculated for the period before and after withdrawal for each subject. This depends upon the length of time before and after withdrawal. Denote these as $y1_hat$ and $y2_hat$. The design matrices for an individual patient are modified to assign the withdrawing patient to the desired treatment arm for the observed or unobserved period. This depends on the missing data imputation methods. If it is the pattern mixture model, patients will be imputed according to the group they were randomized to. For control-based model, both placebo and treatment patients will be imputed using the estimated coefficients pertaining to the placebo group. Then according to the derivation for the conditional distribution $Y2|Y1$, we can sample using the following statement: `rand('NEGATIVEBINOMIAL',(invK_hat+y1_hat)/(invK_hat`

+y1_hat + y2_hat), invK_hat + y1) where invK_hat is the inverse of the sampled dispersion parameter, and y1 is the actual count before withdrawal. The entire number of exacerbations (observed and unobserved) is then: y1 + rand('NEGATIVEBINOMIAL',(invK_hat+y1_hat)/(invK_hat +y1_hat + y2_hat), invK_hat + y1). The sample code is provided below.

```
%let rn=40;

proc surveysselect data=ckout seed=23 method=srs n=&rn out=cksamples; run;

data cksamples2(keep=Intercept mtx mst1 mreg1 mreg2 mx Dispersion _imputation_);set
cksamples;by iteration;
_imputation_+1;
run;

data ckrep(drop=mtx mst1 mreg1 mreg2 mx);
set ck1;
do _imputation_=1 to &rn;
output;
end;
run;

proc sort data=ckrep;by _imputation_;run;
proc sort data=cksamples2;by _imputation_;run;
data ckrep2;merge ckrep(in=a) cksamples2(in=b);by _imputation_;if a=1 and b=1;run;

data ckrepimp(drop=td lin rate1 rate2 k ratep kp p ad);set ckrep2;
if ext=0 then do;
td=plandur-aval;
lin=Intercept+mtx*txval+mst1*st1val+mreg1*reg1val+mreg2*reg2val+mx*xval;
rate1=exp(lin);
rate2=rate1;
if (Dispersion<=0.00000001) then k=100000000;
else k=1/Dispersion;
ratep=rate2*(1+k*ASEQ)/(1+k*rate1*aval);
kp=k/(1+k*ASEQ);
```

```
p=1/(1+kp*ratep*td);  
ad=RAND('NEGBINOMIAL',p,1/kp);  
aseqplus=aseq+ad;  
end;  
else aseqplus=aseq;  
ad=aseqplus-aseq;  
run;
```

3. These imputed numbers are then analysed in a new series of further GENMOD runs (one for each draw), using the model for the primary analysis. However an offset will now be the log of planned treatment period. Derived parameters from the model such as least squares means for treatment and their differences. The sample SAS code is

```
proc genmod data=ckrepimp;  
  by _imputation_;  
  model aseqplus =txval st1val reg1val reg2val/ dist=negbin link=log  
offset=logplanneddur;  
  ods output ParameterEstimates=Pest;  
run;
```

4. Then we combine across imputation data sets using Rubin's formula using the MIANALYZE procedure. These and their confidence interval limits are then exponentiated to derive relative rates. Of note, the rule will be applied on the log risks and log risk ratio.

```
proc sort data=pest out=pest2;by Parameter _imputation_;run;  
proc mianalyze data=pest2;  
  by Parameter;  
  modeleffects estimate;  
  stderr stderr;  
  ods output ParameterEstimates=pout;  
run;
```

```
/* estimated RR and corresponding 95% CI */
```

```
data pouttx;  
  set pout;  
  if Parameter="txval";  
  rr = exp(estimate);
```

```
rrL = exp(lclmean);  
rrU = exp(uclmean);  
run;
```

5. For control-based PMM-MI, we will replace the following command in Step 2 under “**data** ckrepimp”

```
lin=Intercept+mtx*txval+mst1*st1val+mreg1*reg1val+mreg2*reg2val+mx*xval;  
by
```

```
lin=Intercept+0*txval+mst1*st1val+mreg1*reg1val+mreg2*reg2val+mx*xval;
```

This way, we will use the control rate to impute the missing data.

6. For tipping-point analysis, we will replace the following command in Step 2 under “**data** ckrepimp”

```
lin=Intercept+mtx*txval+mst1*st1val+mreg1*reg1val+mreg2*reg2val+mx*xval;  
by
```

```
lin=Intercept+(mtx+delta)*txval+mst1*st1val+mreg1*reg1val+mreg2*reg2val+mx*xval;
```

where “delta” is a sequence of positive numbers representing the diminishing treatment effect for patients in the treatment group needing imputation. A table of p-values for the treatment effect in the analysis model with the imputed data and the “delta” value will be provided.

Change from baseline in FEV1

Pattern mixture model by multiple imputation

1. Partially impute data using Markov Chain Monte Carlo (MCMC) method to obtain 40 datasets with monotone missing pattern:

```
proc mi data=&DSTIN seed=&seed nimpute=40 out=monotone;  
  mcmc impute=monotone;  
  var base &chg_all;  
run;
```

where &chg_all includes change from baseline in FEV1 at all visits.

2. For each of the imputed dataset with monotone missing pattern, the remaining missing data will be imputed by a regression model

```
proc mi data=monotone seed=&seed nimpute=1 out=data_imp;
  by _imputation_;
  class trt01pn sex eosbgp1n cntygr1 endtrs1;
  var sex hgtbl eosbgp1n cntygr1 trt01pn endtrs1 base
      &chg_all;
  monotone reg;
run;
```

3. Analyze the 40 imputed datasets by the ANCOVA model described in [Section 2.4.4.2](#):

```
proc mixed data=data_imp method=reml;
  by _imputation_;
  class usubjid trt01pn sex cntygr1 eosbgp1n avisitn;
  model chg12 = trt01pn sex hgtbl cntygr1 eosbgp1n avisitn
      trt01pn*avisitn base base*avisitn /ddfm=kr residual;
  repeated avisitn / subject=usubjid type=un;
  lsmestimate trt01pn*avisitn 'Tx wks 16-24 avg minus pbo wks 16-24 avg' 0 0
1 1 1 0 0 -1 -1 -1 / divisor=3;
  lsmeans trt01pn*avisitn / pdiff cl e;
  ods output LSMeans=LSMeans_imp Diff=Diff_imp
LSMEstimates=LSMEstimates_imp;
run;
```

4. Apply Rubin's rule to combine analysis results:

```
proc sort data= LSMEstimates_imp;
  by trt01pn _imputation_;
run;

proc mianalyze data= LSMEstimates_imp;
  modeleffects estimate;
  stderr stderr;
  ods output ParameterEstimates=LSMEstimates_Res;
run;
```

Pattern mixture model by control-based multiple imputation

This approach is similar to the standard method described above, except for Step 2. After obtaining datasets with monotone missing patterns in Step 1, the following steps will be repeated to sequentially impute missing data at each time point:

- 1) For time point t , separate the imputed datasets into two parts: `imp_&t`, containing all placebo patients and those from the active treatment groups that have missing change from baseline in FEV1 at time t ; and `rest_&t`, containing the rest of the patients from the active treatment groups.
- 2) Impute missing values at t based on the model estimated from placebo group patients:

```
proc mi data=imp_&t seed=&seed.&t nimpute=1
  out=imputed_&t;
```

```
by _imputation_;  
class sex eosbgpln cntygr1 endtrs1;  
var sex hgtbl eosbgpln cntygr1 endtrs1 base  
    &chg_prior chg_&t;  
monotone reg (chg_&t);  
run;
```

where `chg_&t` is change from baseline in FEV1 at t and `&chg_prior` includes change from baseline in FEV1 at all visits prior to t . No prior value will be included when imputing the first post-randomization time point.

- 3) Combine the imputed data `imputed_&t` with `rest_&t`.

Signature Page for VV-CLIN-0547342 v1.0
act15104-16-1-9-sap

Approve & eSign	
-----------------	--

Approve & eSign	
-----------------	--

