1.3 DETERMINATION OF SAMPLE SIZE

To assess the power of the primary efficacy endpoint the annualized rate of moderate-to-severe AECOPD, we assume

- Average of 1.0 to 1.5 AECOPD per year in the placebo group of this study population enriched for severity and high risk of AECOPD.
- The number of AECOPD follows a negative binomial distribution with dispersion parameter 1.5 for all the groups.
- A Wald-test is used to test whether the risk ratio is 1 with 2-sided 5% significance level.
- Patients will be treated with a minimum of 24 weeks and a maximum of 52 weeks depending on their study entry times. The monthly cumulative patient accruals are assumed to be 1, 5, 10, 25, 50, 90, 150, 210, 270, 335 and 340 for an eleven (11)-month accrual period.

- Cumulatively, 9%, 15% and 20% of patients drop out of the study due to discontinuation or other reasons by 12, 24 and 52 weeks after study entry.
- Patients are randomized to the treatment group and the placebo group with a 1:1 ratio.

With these assumptions and 170 patients per group (340 patients in total), the study will yield 81.6% to 88.8% powers with risk reduction equal to 45% in rate of AECOPD and the placebo rate ranging from 1.0 to 1.5 per year. To obtain at least 80% power, the minimum risk reduction is from 44.2% to 40.6%. The minimum detectable risk reduction (i.e. with 50% power) is from 32.7% to 30.0%. See the table below for more details.

Table 1 - Power calculation for various AECOPD event rates in the placebo group

Placebo rate	Power for certain Risk Reduction (RR)			Minimum RR for certain power	
	RR=40%	RR=45%	RR=50%	Power=80%	Power=50%
1.0	69.9%	81.6%	90.3%	44.2%	32.7%
1.2	74.1%	85.2%	92.9%	42.5%	31.4%
1.5	78.5%	88.8%	95.2%	40.6%	30.0%

RR: risk reduction

Based on the accrual and drop-out assumptions, the mean exposure time is 35.5 (\pm 12.8) weeks. Since we use variable follow-up times for patients entering at different times, the power will depend on the actual accrual rates and the drop-out rates. We will closely monitor these rates. If the accrual rates are significantly lower than planned and/or the drop-out rates are higher than expected, the minimum treatment period may be extended to achieve the desired amount of total exposure. The maximum treatment period of 52 weeks will not be changed.

To assess the key secondary efficacy endpoint, the change from baseline to Week 24 in pre-bronchodilator FEV1, we assume that:

[figure not shown]

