If the model fails to achieve convergence, different estimation algorithms will be applied in the order: default→LAPLACE→QUAD. If the issue still exists, other handling may be considered. The adjustment will be added to the footnote of the corresponding outputs. The gross estimates of the annualized event rates will also be presented by treatment group. Mean cumulative function plot will be provided for descriptive purposes.

Similar analysis will be performed for the secondary efficacy population (high EOS group), without the baseline eosinophil strata in the model.

Estimated clinical efficacy of SAR440340 versus placebo

An analysis to assess the efficacy of SAR440340 if patients adhere to the treatment as directed will also be conducted. In this approach, off-treatment measurements of exacerbation events from patients who prematurely discontinue treatment will be excluded from the analysis. Negative binomial model with the same set of covariates as specified in the primary analysis will be used. The offset will be log-transformed on-treatment duration, which is defined as the duration from the first dose to the last dose +14 days within the observation duration. This approach defines the estimand of the efficacy of SAR440340 with treatment adherence. Similar analysis will be performed for the secondary efficacy population (high EOS group), without the baseline eosinophil strata in the model.

Missing data handling

If patients withdraw from the study before completing the planned treatment durations, exacerbation events that may occur after study discontinuation will not be observed. These patients are considered as patients with missing data on exacerbation. Number of patients with missing data, reasons and timing of study withdrawals will be summarized by treatment groups. Summary statistics of selected demographic and baseline disease characteristics will be provided for patients with missing data and patients with complete data separately. Graphical summaries of the dropout patterns such as Kaplan-Meier plots of time to study discontinuation with different reasons of discontinuation may be provided to examine if there is any different missing data pattern between treatment groups. In addition, the following sensitivity analyses will be conducted to assess the robustness of the conclusion of the main model.

- ***Pattern mixture model - multiple imputation (PMM-MI)***

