For each patient with missing data of exacerbation events, the number of events that could occur in the period from study discontinuation to the end of planned treatment duration will be estimated based on a negative binomial regression model using observed data with adjustment of the treatment group, region (pooled country), baseline eosinophil strata, number of severe exacerbation events within 1 year prior to the study, smoking history (current vs. former smoker) and post-BD FEV1 percent predicted (<50% vs. ≥50%) at baseline. The period from study discontinuation to the end of planned treatment duration will be the exposure time. Once the number of events in the period is imputed, the total number of events in the planned treatment duration will enter the negative binomial regression model as described in the primary analysis with the offset equal to the log-transformed planned treatment duration.

- ***Control-based PMM-MI***

For each patient with missing data of exacerbation events, the number of events that could occur in the period from study discontinuation to the end of planned treatment duration will be estimated based on the same negative binomial regression model mentioned in the previous bullet point,

except the imputation will be based on the estimate of the control group only. Once the number of events in the residual treatment duration is imputed, similar model as in the PMM-MI will be used.

- ***Tipping point analysis***

For each patient with missing data of exacerbation events, the number of events that could occur in the residual treatment duration will be estimated in a similar fashion as PMM-MI, based on various event rates. If the patient is on SAR440340, the event rate will be increased and if the patient is on placebo, the event rate will not be changed. The adjusted rate will then be used to impute the number of events that would occur in the period with missing data. A sequence of increasing event rates will be used to generate different imputed datasets.

Similar analyses will be performed for the secondary efficacy population (high EOS group), without the baseline eosinophil strata in the model.

Technical details on missing data handling are provided in [Appendix J](#).

Subgroup analysis

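### SAP Appendix J, step 2 specifies two different draws for missing exacerbation counts: the text uses the inverse dispersion correctly, but the sample code inverts the dispersion and then uses the result as the dispersion

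*SAP*

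**What the plan says.** SAP section 2.4.4.1 plans three analyses for patients who withdraw before the end of their planned treatment duration: PMM-MI, control-based PMM-MI and a tipping-point analysis. It says that "the following sensitivity analyses will be conducted to assess the robustness of the conclusion of the main model". It describes the imputation in outline only and then says "Technical details on missing data handling are provided in" Appendix J.

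Appendix J step 2 gives the draw twice.

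- **Text.** The missing-period count is negative binomial with size invK_hat + y1 and probability (invK_hat + y1_hat)/(invK_hat + y1_hat + y2_hat), "where invK_hat is the inverse of the sampled dispersion parameter, and y1 is the actual count before withdrawal".
- **Code.** It sets "else k=1/Dispersion", with the guard "if (Dispersion<=0.00000001) then k=100000000". It then computes a conditional rate, "ratep=rate2*(1+k*ASEQ)/(1+k*rate1*aval"), a conditional dispersion kp = k/(1 + k·y1), and p = 1/(1 + kp·ratep·td). The draw is "ad=RAND('NEGBINOMIAL',p,1/kp").

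Steps 5 and 6 build the control-based and tipping-point versions by replacing only the linear predictor, so all three analyses use these lines. SAP section 1.3 gives the planning value: "The number of AECOPD follows a negative binomial distribution with dispersion parameter 1.5 for all the groups".

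**The concern.** In the code k is defined as the inverse of the dispersion, but the lines that follow are the standard conditional formulas written for k as the dispersion. The text and the code therefore describe different distributions, and a programmer who copies the block will not carry out what the text specifies.

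The conditional draw decides how far a withdrawing patient's own record informs the imputed count. With the dispersion inverted, that record counts for too little when the true dispersion is above 1 and too much when it is below 1. What is at stake is the accuracy of the analyses that test the primary result against missing data, mainly their standard errors.

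**Working it through.** **Inputs.** Dispersion 1.5, placebo rate 1.0 to 1.5 per year (1.2 used here), accrual and drop-out all come from SAP section 1.3. The formulas come from Appendix J. The observed and missing periods in the examples are illustrative.

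**1. What dispersion means in this plan.** With variance = mu + D·mu² and D = 1.5, a Wald calculation using the stated accrual and drop-out gives mean exposure 35.5 weeks (SD 12.7; SAP 35.5, 12.8). Power for a 45% reduction at placebo rates 1.0, 1.2 and 1.5 is 81.7%, 85.3% and 88.9%, against the SAP's 81.6%, 85.2% and 88.8%. With D = 1/1.5 it is 90.9%, 94.0% and 96.7%, which does not match. So 1.5 is the dispersion, not its inverse.

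**2. Algebra of the code.** Write mu1 and mu2 for the expected counts in the observed and missing periods.

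- Size: 1/kp = (1 + k·y1)/k = 1/k + y1.
- kp·ratep·td = k·mu2/(1 + k·mu1) = mu2/(1/k + mu1).
- Hence p = (1/k + mu1)/(1/k + mu1 + mu2).

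With k = D this is exactly the text. With k = 1/D, as printed, the size is D + y1 and p = (D + mu1)/(D + mu1 + mu2). The two agree only at D = 1.

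**3. One patient.** Rate 1.2/year, 12 weeks observed, 28 missing: mu1 = 1.2 × 12/52 = 0.277 and mu2 = 1.2 × 28/52 = 0.646. At D = 1.5:

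- Text mean: (0.667 + y1) × 0.646/(0.667 + 0.277)
- Code mean: (1.5 + y1) × 0.646/(1.5 + 0.277)

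| Events observed | Text | Code |
|---|---|---|
| 0 | 0.46 | 0.55 |
| 1 | 1.14 | 0.91 |
| 2 | 1.83 | 1.27 |

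After two events the variance is 3.08 by the text and 1.74 by the code.

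**4. Which is right.** A gamma-Poisson simulation of 4 million patients (D = 1.5, 1.2/year, 12 weeks observed, 40 missing) gave true conditional means 0.652, 1.629 and 2.603 after 0, 1 and 2 events. The text gives 0.652, 1.630 and 2.609. The code gives 0.779, 1.299 and 1.818.

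**5. The guard.** A very large k is the correct limit for an inverse dispersion. Used as a dispersion, it is extreme overdispersion. In the step 3 example the near-Poisson mean should be 0.65 whatever the history; the code gives about 0 after no events and 28/12 = 2.33 after one.

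**6. Average imputed count.** The imputed mean is (1/k + y1)·mu2/(1/k + mu1). If y1 has expectation mu1, as in PMM-MI, this averages to mu2 for any k. Under step 5 it does not: the placebo rate enters mu1, while an active patient's y1 arises at the active rate. With 0.66/year in the active arm (1.2 × 0.55), the expected y1 is 0.152. The average is then 0.646 × (0.667 + 0.152)/(0.667 + 0.277) = 0.561 by the text and 0.646 × (1.5 + 0.152)/(1.5 + 0.277) = 0.601 by the code.

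**7. Trial level.** Simulated trials had 170 per arm, 1.2/year on placebo, rate ratio 0.55, 40 imputations, a treatment-only refit and Rubin pooling. There were 1000 trials at D = 1.5 and 600 at 0.5, with corrected and printed k run on the same trials and parameter draws. Mean exposure was 35.0 weeks (SD 12.6). Posterior draws used a normal approximation.

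| | PMM-MI | Control-based |
|---|---|---|
| Rate ratio, D = 1.5, corrected / printed | 0.544 / 0.544 | 0.584 / 0.590 |
| Change in pooled SE, D = 1.5 | −2.5% | −3.4% |
| Significant, D = 1.5, corrected / printed | 86.7% / 88.4% | 79.7% / 81.2% |
| Change in pooled SE, D = 0.5 | +6.1% | +8.7% |

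**The case against.** Appendix J calls its code explanatory. That is fair as far as it goes, but the caveat is tied to covariates that may change between models. It does not cover the distribution drawn from, and section 2.4.4.1 gives no other specification of the draw.

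The sampled column might already hold the inverse. Step 1 says that the dispersion parameter itself is sampled, and if it were inverted the text formula would be wrong instead. The contradiction would remain.

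The effect is small. This stands. At dispersion 1.5 the slip changes PMM-MI significance in 2.1% of simulated trials, against 1.4% from re-running the corrected draw with another seed. SAP section 2.4.4.4 makes all p-values nominal, and the correct formula is printed just above the code.

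The simulation omits the planned covariates. This also stands. If those covariates are prognostic, residual dispersion would be below the marginal value and could lie nearer 1, where text and code agree. The documents do not give it.

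The guard is not a second error. This is correct: it fits the definition of k, and the slip lies in the lines after it.

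**Conclusion.** Step 2 contradicts itself, by algebra that needs no assumed values. The text is right and the printed code is wrong unless the dispersion is 1. The severity is minor.

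The per-patient figures rest on the planning dispersion and the illustrative periods. The standard-error figures rest on the treatment-only simulation. In the planned covariate-adjusted model both their size and their sign depend on the residual dispersion.

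Three stronger readings are tempting but not supported.

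- A reader might infer that the primary result is affected. It is not: the primary analysis uses observed events with observation time as offset and no imputation.
- A reader might infer that the slip always makes the sensitivity analyses too lenient, or that it never moves the rate ratio. The standard-error change reverses below dispersion 1. The rate ratio is unmoved under PMM-MI only; the control-based one shifts slightly.
- A reader might infer that step 6 misplaces the tipping-point shift because it enters the observed period as well as the missing one. Step 2 allows the design to be modified for either period, so this is at most a labelling note.

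**What to change.** Make the code agree with the text, in one of two ways:

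- set k equal to the sampled dispersion, and when it is at or below 0.00000001 make a Poisson draw with mean rate2 × td; or
- keep k as the inverse, guard included, and replace the lines for ratep, kp, p and the draw with the text's own formula: `RAND('NEGBINOMIAL',(k+rate1*aval)/(k+rate1*aval+rate2*td),k+ASEQ)`.

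Either change carries through to the control-based and tipping-point analyses and to their repeats in the high-eosinophil population. The cost is a few lines of SAP sample code. The primary analysis and the conduct of the trial do not change.

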2.4.4.4 Multiplicity issues

No adjustments for multiplicity are planned for this Phase 2a study. More specifically, no adjustments will be made in comparing the two treatment groups based on the secondary efficacy endpoints and no adjustments will be made for the subgroup analyses. All reported p-values will be nominal.

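### Tipping-point code (SAP Appendix J, step 6) adds delta to the observed-period rate as well, so each tabulated delta applies a somewhat milder penalty than exp(delta)

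*SAP*

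**What the plan says.** SAP section 2.4.4.1 lists a tipping-point analysis among the missing-data sensitivity analyses for the primary endpoint. For SAR440340 patients with missing follow-up the event rate is raised; for placebo patients it is left alone. The section states the purpose of the raised rate: "The adjusted rate will then be used to impute the number of events that would occur in the period with missing data". On how the penalty is to be varied from one run to the next, it adds: "A sequence of increasing event rates will be used to generate different imputed datasets".

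Appendix J gives the mechanics. Step 2 keeps separate expected counts for the time before and after withdrawal and draws the missing count conditionally on the observed one. In code, `rate1` (before) is exp(`lin`), `rate2` (after) is set equal to `rate1`, and the conditional rate is "ratep=rate2*(1+k*ASEQ)/(1+k*rate1*aval"), where `aval` is the observed time and `ASEQ` the observed count. Step 6 replaces only `lin`, by "lin=Intercept+(mtx+delta)*txval" plus the covariate terms. Its output is "A table of p-values for the treatment effect in the analysis model with the imputed data", set against delta.

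**The concern.** Because step 6 alters `lin` and nothing restores an unshifted `rate1`, delta enters the numerator of the conditional rate (as intended) and also its denominator, through the expected count in the observed period. Raising that expected count makes the patient's actual count look low for someone with that rate. The conditional update then pulls the imputed rate back down, which undoes part of the penalty.

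A tipping-point table is read by asking how bad withdrawn drug patients would have to be before significance is lost. If each row applies less than it appears to, significance is lost at a larger delta and the result looks more robust than it is, in the drug's favour. The applied penalty also differs between patients, so a row has no single meaning on the rate scale.

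**Working it through.** **Planning inputs (SAP 1.3).** 170 per arm; dispersion 1.5; placebo rate 1.0 to 1.5/yr; 45% reduction; the stated 11-month accrual; dropout 9%, 15% and 20% by Weeks 12, 24 and 52; treatment for 24 to 52 weeks. With uniform entry within months, uniform dropout within intervals and a negative binomial Wald test, these give mean exposure 35.5 weeks (SD 12.8) and power 81.6%, 85.2% and 88.8% at placebo rates 1.0, 1.2 and 1.5. All match the SAP.

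**Applied factor.** Let D = exp(delta), r the patient's fitted drug rate, a the observed time in years and y the observed count.

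- As coded: D·r·(1+k·y)/(1+k·D·r·a)
- Delta in the missing period only: D·r·(1+k·y)/(1+k·r·a)
- With no delta: r·(1+k·y)/(1+k·r·a)

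Dividing the first by the third, the coded factor is D·(1+k·r·a)/(1+k·D·r·a). For D>1 and a>0 this is below D, and it cannot exceed 1+1/(k·r·a). Dividing the second by the third gives exactly D.

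**Two values of k.** The code prints "else k=1/Dispersion", which is 0.667 at the planning dispersion. The step 2 text uses a negative binomial size of `invK_hat`+y, "where invK_hat is the inverse of the sampled dispersion parameter". The coded size is 1/k+y, so text and code agree only if k is the dispersion itself, 1.5. That mismatch is a separate matter. It changes the size of the present effect but not its direction, so both values are shown.

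**Typical dilution.** Take r = 1.2 × 0.55 = 0.66/yr. Under the planned accrual and dropout, 18% withdraw early. Of these, 84% leave before Week 24 and hold 94% of the missing time; the median withdrawal time weighted by missing time is 8.7 weeks. The SAP lists no delta values, so the multipliers are assumptions; ×1.82 is 1/0.55, full loss of effect.

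| Nominal D | Average applied, k=0.667 | Average applied, k=1.5 | Week 24 withdrawal, k=0.667 |
|---|---|---|---|
| 1.82 | 1.71 | 1.62 | 1.60 |
| 4 | 3.3 | 2.85 | 2.7 |
| 8 | 5.5 | 4.3 | 3.7 |

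Averages are weighted by missing time. Check of one cell at Week 24: a = 24/52.18 = 0.46 yr, k·r·a = 0.667 × 0.66 × 0.46 = 0.202, and 4 × 1.202/(1 + 4 × 0.202) = 2.66.

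**Trial-level effect.** This was simulated at placebo 1.2/yr: 1,511 trials, 40 imputations, Rubin's rules, and the SAP covariates with assumed prevalences and no covariate effects. Simulated power was 84.6% against the SAP's 85.2%. The entries are the share of all trials keeping p<0.05 with delta in both periods, against the missing period only.

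| Nominal D | k=0.667 | Gap, points (SE) | k=1.5 | Gap, points (SE) |
|---|---|---|---|---|
| 1.82 | 75% v 73% | 2.0 (0.4) | 75% v 72% | 3.6 (0.5) |
| 4 | 47% v 33% | 14.0 (0.9) | 52% v 30% | 22.6 (1.1) |
| 8 | 16% v 4% | 11.6 (0.8) | 24% v 4% | 20.7 (1.0) |

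At placebo 1.0 and 1.5/yr, with k=0.667, the gap is 1.7 points at ×1.82 for both rates, and 9 and 17 points at ×4. On the grid 1.82, 2, 3, 4, 5, 8 (k=0.667), the median first value at which significance is lost is 4 under both codings at 1.0/yr, and 5 against 4 at 1.2 and 1.5/yr.

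**The case against.** **The contradiction is inferred.** Section 2.4.4.1 says the imputation resembles the standard pattern-mixture one, which uses one rate for both periods, and Appendix J describes delta as a loss of effect for the patient. No passage calls exp(delta) the missing-period multiplier. So one could read step 6 as a coherent patient-level shift. This has some force: the SAP never states what delta multiplies. But section 2.4.4.1 uses the adjusted rate to impute the missing period and promises a sequence of rising event rates, and the coded version gives no common rate multiplier. Appendix J also calls its code explanatory. That remark mainly concerns covariates, and step 6 is the only operational definition of delta.

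**Step 5 has the same structure.** It does, and a reader might infer that it is wrong too. The documents do not support that: Appendix J allows a withdrawing patient to be assigned to the desired arm for the observed or unobserved period, so using the placebo rate in both is a permitted choice. As printed, step 6 runs continuously from no shift to step 5 (delta = -`mtx`), and a correction gives up that link.

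**The effect is small where it matters.** Diminishing effect runs naturally up to full loss, where the gap is 2 to 4 points. At ×4 withdrawn drug patients would have 4 × 0.66 = 2.6 events/yr against 1.2 on placebo, which is assumed harm. This stands, and it sets the priority.

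**Conclusion.** The point holds as a low-priority correction to one sensitivity analysis. Step 6 applies less than exp(delta) for every positive delta, by an amount that varies with the patient's observed time and fitted rate, and always in the drug's favour. The direction is algebraic and holds for either k. The sizes rest on the planning assumptions and on an assumed grid.

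A reader might go further and infer that severe penalties can never be reached, or that the table would have to show about ×10 to apply ×4. At Week 24 both are true: the ceiling with k=1.5 is 1+1/0.455 = ×3.2, and with k=0.667 applying ×4 needs 4/(1 - 0.202 × 3) = ×10.2. But that is a late withdrawal. Most of the missing time belongs to much earlier withdrawals, and at Week 12 the k=1.5 ceiling is already ×5.4.

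Nor do the documents support reading this as a threat to the main result. The primary analysis does not use this code, "All reported p-values will be nominal" (SAP 2.4.4.4), and neither document ties a decision rule to the tipping point.

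**What to change.** In step 6, leave `lin` and `rate1` as in step 2, without delta, and set `rate2=rate1*exp(delta*txval)`. The factor on the imputed rate is then exactly exp(delta) for every drug patient, and placebo patients are unchanged. Label exp(delta) in the p-value table as the missing-period rate multiplier, and list the delta values to be used. Leave step 5 as it is.

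The cost is one changed line of code, a table label and a footnote. The footnote should say that delta = -`mtx` no longer reproduces step 5 exactly; the difference in share significant is about 2 points with the printed k and 3 to 4 with k equal to the dispersion. Tipping points will come out somewhat less favourable to the drug.
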